Recruitment rates at the eight active sites will be closely monitored during this phase. The initial eight sites are each expected to enroll 36 participants in the first year of the study, for a total of 288 participants at the end of the first year. The actual recruitment experience of the eight sites in the first year will be used to revise the projected recruitment rate for the remainder of the study and may lead to a lengthening or shortening of the total recruitment period, as appropriate. Measures to address unexpectedly low recruitment rates during this feasibility phase have been described on page 14. At the completion of the feasibility phase, the study will be moved to a continuation phase where the remaining 7 sites will be activated and the remaining participants (1232 participants) will be recruited and followed up.

E. Data Analysis Plan

The primary analysis will be performed to test the null hypothesis of no difference in composite outcome of all-cause mortality, MI, coronary revascularization, acute renal failure, or post-randomization stroke between participants randomly assigned to a 10 gm/dl Hb transfusion strategy compared to participants assigned to 7 gm/dl transfusion strategy. If the null hypothesis is not rejected, a 95% confidence interval will be constructed about the difference observed to inform the medical community as to how large the difference is likely to be in either direction. All statistical tests will be two-sided and the primary outcome will be tested at 5% level of significance. SAS 9.4 or higher will be used to conduct all the statistical analyses. A variety of analytic methods will be used for the primary endpoint, secondary endpoints, tertiary endpoints and other analyses (TABLE 4).

1. Analysis Populations

Intent-to-Treat (ITT) – This population is defined as the population of participants who will be randomized to either of the transfusion strategy groups – Liberal or Restrictive. The participants will be categorized (in terms of their transfusion strategy assignment) based on their initial randomized group and will be included in analyses irrespective of their status – completer or drop out of the study before completion. The testing power for the primary endpoint is estimated as 90% in this population.

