The primary study endpoint will be composite outcome of all-cause mortality, MI, coronary revascularization, acute renal failure, or post-randomization stroke within 90 days from randomization. This outcome will be compared according to assigned transfusion strategy (analysis by intent to treat), using Pearson χ^2 test. The test for differences between transfusion strategies in the primary outcome will be conducted at an overall α -level of 0.05. Additional analysis will be conducted using logistic models to adjust for other clinical factors, such as age, RCRI, nadir Hb, and interaction terms. Logistic regression will be used for the primary endpoint ($y = 1$ if a composite outcome, otherwise $y = 0$) analysis with transfusion strategy group as the testing factor (X). The following covariates will be included in the model: age (z_1), RCRI (z_2), nadir Hb(z_3), site (z_4), and the interactions of testing factor with age (w_1), RCRI (w_2) and nadir Hb (w_3). Given the composite outcome probability $p = \Pr(y=1|X, z_1, z_2, z_3, z_4, w_1, w_2, w_3)$, the basic model is defined as follows:

$$\text{Logit}(p) = \ln\left(\frac{p}{1-p}\right) = \beta_0 + \beta_1 X + \beta_2 z_1 + \beta_3 z_2 + \beta_4 z_3 + \beta_5 z_4 + \beta_6 w_1 + \beta_7 w_2 + \beta_8 w_3$$

Odds ratio and 95% confidence interval (CI) will be presented using SAS PROC GENMOD. If the coefficient for treatment effect is significant, then the null hypothesis will be rejected. Logistic models will be tested for goodness of fit. We will assess goodness-of-fit using the statistic -2 log likelihood, which has a chi-square distribution under the null hypothesis that all the explanatory variables in the model are zero. We will also consider the Akaike Information Criterion statistic and the Schwartz Criterion statistic, both of which adjust the -2 log likelihood for the number of items in the model. Models that show lack of fit will be reconsidered for the inclusion of additional variables or use of alternate models with assumptions that are better met by the study data. One alternate model if model fit is poor for logistic regression is a log-linear model.

3. Secondary endpoint analyses

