variable. We will also consider the Akaike Information Criterion statistic and the Schwartz Criterion statistic, both of which adjust the -2 log likelihood for the number of items in the model. Models that show lack of fit will be reconsidered for the inclusion of additional variables or use of alternate models with assumptions that are better met by the study data. One alternate model if the model fit is poor for logistic regression is a log-linear model. For logistic regression analysis, if the coefficient for intervention effect is significant (i.e., the confidence interval for the odds ratio does not include 1), then the null hypothesis of no intervention effect adjusting for other covariates in the final model will be rejected. The P value for testing each covariate coefficient in the model being zero will be based on Wald test (Table 17a-e). The primary analysis will be done in the ITT population. Additional analyses will be done in the mITT, No-Recent-Transfusion, Completers, and Per Protocol populations.

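### The Protocol lets a significant coefficient in the additional logistic model reject the primary null, and neither document says that the Pearson test alone decides

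*Protocol*

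**What the plan says.** - **The null.** Protocol XVI.E defines one treatment null: "The primary analysis will be performed to test the null hypothesis of no difference in composite outcome". It adds: "All statistical tests will be two-sided and the primary outcome will be tested at 5% level of significance".
- **The first test.** Protocol XVI.E.2: "This outcome will be compared according to assigned transfusion strategy (analysis by intent to treat), using Pearson" chi-square. The alpha sentence follows at once: "The test for differences between transfusion strategies in the primary outcome will be conducted at an overall α -level of 0.05".
- **The second test.** The same section continues: "Additional analysis will be conducted using logistic models to adjust for other clinical factors". The model contains strategy, age, RCRI, nadir Hb, site, and the interactions of strategy with age, RCRI and nadir Hb. Its level is implied by "Odds ratio and 95% confidence interval (CI) will be presented using SAS PROC GENMOD". Its decision rule is "If the coefficient for treatment effect is significant, then the null hypothesis will be rejected".
- **Table 4 of the Protocol** lists Pearson and logistic regression as methods 1 and 2 under the primary endpoint, without ranking them.
- **SAP 7.1** keeps Pearson first, adds a site-stratified Cochran-Mantel-Haenszel (CMH) test, and keeps the logistic model as additional. If the odds-ratio interval excludes 1, "then the null hypothesis of no intervention effect adjusting for other covariates in the final model will be rejected". A model with poor fit may be given more variables or replaced.
- **SAP 7 (introduction)** defines the primary analysis by endpoint and population, not by test.

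**The concern.** An overall alpha belongs to a decision, and the decision here has two written routes. XVI.E.2 contains one explicit rejection rule, and it is attached to the logistic model, not to Pearson. The only treatment null defined up to that point is the primary one. No order, gatekeeping or split of alpha links the two tests.

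This matters when they disagree. Suppose Pearson gives p = 0.06 and the adjusted model p = 0.04. Read literally, the Protocol rejects the primary null. Read with the SAP, only an adjusted null is rejected. If Pearson decides, nothing is rejected. The choice among these readings should not be open once the data are known, least of all when the adjusted model itself can be revised after inspection.

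**Working it through.** **1. The plan's own figure.** Inputs from Protocol XVI.B: 30% against 22.5%, two-sided 0.05, 90% power, 5% dropout. Pooled-variance formula for two proportions, no continuity correction, mean rate 0.2625:

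n per arm = [1.960 × √(2 × 0.2625 × 0.7375) + 1.282 × √(0.30 × 0.70 + 0.225 × 0.775)]² / 0.075² = (1.2196 + 0.7945)² / 0.005625 = 721.2, so 722.

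The total is 1444, and 1444 / 0.95 = 1520. Both match. The trial is therefore sized for one unadjusted test at 0.05.

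**2. If Pearson alone decides.** Alpha is 0.05. Three interim looks at |Z| > 4.0 (SAP 5.5.2) add at most 3 × 0.000063 = 0.0002.

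**3. If either test may reject.** For two two-sided 0.05 tests whose statistics have correlation ρ under the null, the chance that at least one rejects (bivariate normal) is:

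| ρ | Either rejects |
|---|---|
| 0 | 1 − 0.95² = 9.75% |
| 0.90 | 7.04% |
| 0.95 | 6.46% |
| 0.98 | 5.93% |
| 1 | 5.00% |

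**4. Where ρ falls.** Null simulation with 1520 participants, 15 sites, 30% events and 6,500 trials per row (Monte Carlo SE about 0.3 points).
- From the Protocol (II.b and II.c): RCRI odds ratios 1.8, 2.07 and 2.38; Hb odds ratio 0.72 or 0.566.
- Assumed: age odds ratio 1.03 per year, age mean 69 (SD 8), Hb mean 8.7 (SD 0.8), RCRI class mix 15/35/30/20%, between-site SD 0.25 on the log-odds scale. Hb is not affected by arm.

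| Covariate effects | Pearson alone | Pearson or main-effects logistic | Pearson or interaction model, centred | Pearson or interaction model, uncentred |
|---|---|---|---|---|
| Hb OR 0.72 | 5.0% | 6.3% | 6.3% | 9.5% |
| Hb OR 0.566 | 5.4% | 6.9% | 7.1% | 10.0% |
| Hb OR 0.72, all covariate effects × 0.3 | 4.9% | 5.9% | 5.9% | 9.6% |

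Correlation with Pearson is 0.96–0.99 for the main-effects model and 0.05–0.08 for the uncentred interaction model. In the latter, the arm coefficient is the effect at age 0 and Hb 0, so it is almost unrelated to the overall comparison. The documents do not mention centring.

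Other assumptions change the level more than the gap. With 722 per arm, age and Hb odds ratios per SD of 1.3 and 0.80 (weak) or 1.6 and 0.57 (strong), and site SD 0.2 or 0.4, 8,000 trials each gave 6.2% and 6.6% for either test, against 5.0% and 4.6% for Pearson. A further run gave 5.2–6.3% against 4.2–4.4%, and about 9–10% with uncentred interactions.

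**5. Timing of nadir Hb.** Protocol XVI.A expects the restrictive group's nadir to reflect its transfusion trigger, which suggests a post-randomization value. The title of SAP Table 17 puts the word baseline before age, RCRI and nadir Hb, which can be read the other way. If the value is taken after randomization and is 0.5 gm/dl lower in the restrictive arm (assumed), with no effect of arm on outcome, the main-effects logistic test alone rejects in 27% (Hb OR 0.72) to 65% (Hb OR 0.566) of trials.

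**The case against.** The strongest reply is that the hierarchy is already there. Both documents put Pearson first and call the logistic model additional. The Protocol's alpha sentence speaks of one test and directly follows Pearson. The sample size comes from an unadjusted comparison. The SAP, where the Protocol says departures from its statistical plan will be specified, replaces the general null with one that is conditional on covariates. On that reading 0.05 is delivered, and the Protocol sentence is loose wording about a supportive model.

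Much of this stands. It is good evidence of intent, and it makes Pearson the natural choice as sole decider. The CMH test must also be left out of the error count, because neither document gives it a rejection rule. The simulated main-effects model is not exactly either planned model: it includes site, which the SAP's model does not list, and omits the Protocol's interactions. Its figures are therefore illustrative.

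The reply does not remove the Protocol sentence, which is unqualified and still current. The SAP does not withdraw it or state which test governs. In SAP 7.1 the alpha sentence follows both Pearson and CMH, so its position there is less decisive than in the Protocol.

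**Conclusion.** The point holds as an unresolved decision rule: a written sentence can yield a rejection that the stated alpha does not cover. Applied literally, it raises the false-positive rate by about 1 to 2 points with a main-effects or centred interaction model, to about 6–7%. With the uncentred interaction model the rate is about 9–10%. These figures depend on assumed age effects, site variation, Hb distribution and RCRI mix. The much larger figures for a post-randomization nadir Hb also depend on an assumed 0.5 gm/dl difference between arms and on a timing that the documents do not settle.

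A reader might infer that the trial's alpha of 0.05 is lost, or that the sponsor plans to claim success from the adjusted model. The documents support neither. If Pearson alone decides, 0.05 holds, and no passage states an intention to rely on the adjusted result. Nor is CMH a third route to rejection.

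**What to change.** - In Protocol XVI.E.2 and SAP 7.1, state that the Pearson test in the ITT population alone decides the primary hypothesis at two-sided 0.05.
- Delete the Protocol's rejection sentence for the logistic coefficient. Reword the SAP's sentence so that it concerns only the supportive adjusted estimate.
- Report the logistic and CMH results as supportive, with 95% confidence intervals for the estimates. Neither may reject or rescue the primary null.

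The cost is a few sentences, and the sample size stays at 1444 evaluable and 1520 randomized. The sponsor could not claim success from an adjusted result when Pearson is not significant.

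Keeping both routes and splitting alpha at 0.025 each would cost more. With 2.241 in place of 1.960, n per arm = (1.3947 + 0.7945)² / 0.005625 = 852.1, so 853. That is 1706 evaluable, or about 1796 randomized (1706 / 0.95). At the planned 1444 evaluable, Pearson power would fall from 90.0% to 84.2%.

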In order to estimate 90 day composite endpoint rate (defined in Section V) after surgical interventions in the VA population, we conducted an analysis of Vascular and General Surgery operations identical to those targeted in the proposed trial as described in pages 5-7. Data of 171,357 VA patients who underwent these vascular or general procedures and had available nadir Hb level from the Corporate Data Warehouse (CDW) database was used for this analysis. We anticipate in the proposed trial the nadir Hb in the restrictive transfusion group to range between 6-9 gm/dl (transfusion trigger Hb < 7 gm/dl). Our database review revealed that 29.8% out of 25,343 patients who were at high cardiac risk and had nadir postoperative Hb at this range developed the composite endpoint of death, MI, acute renal failure, or coronary revascularization within 90 days from the index operation. The breakdown of event rates for the individual components of the composite endpoint is shown in Table 2 . Based on the analysis, a baseline event rate of 30% for the composite endpoint is expected in the restrictive group.

B. Sample Size Calculation and Power Analysis

The sample size estimation and power analysis are based on the hypothesis testing of the primary composite endpoint, which is the most important measure proposed in the study. According to the analysis of event rates outlined in the previous section, we assume that 30% rate for the primary endpoint can be anticipated in the restrictive transfusion group. We also assume a 25% reduction or 22.5% event rate in the liberal group. The sample size for the study is estimated based on a superiority trial design. To detect the expected 7.5 percentage point difference or 25% reduction, a sample size of 1444 will be required at 90% power, 5% type-I error rate and with a two-sided test (TABLE 3). Assuming 5% dropout rate, then 1520 participants (or 760/group) will be needed to achieve the desired testing power.

TABLE 3 Sample Size Estimation and Power Analysis

90 Day Composite Endpoint (%)				Power (%)			
Liberal	Restrictive	Difference	Percent Difference	75	80	85	90
17.50	25.00	7.50	30.0	826	932	1066	1248
18.75	25.00	6.25	25.0	1214	1372	1570	1836
20.00	25.00	5.00	20.0	1936	2188	2502	2928
21.00	30.00	9.00	30.0	650	734	840	982
22.50	30.00	7.50	25.0	954	1080	1234	1444
24.00	30.00	6.00	20.0	1520	1718	1964	2298
24.50	35.00	10.50	30.0	526	594	678	794

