7.1. Primary Endpoint Analysis

The primary study endpoint will be a composite outcome of all-cause mortality, MI, coronary revascularization, acute renal failure, or post-randomization stroke within 90 days from randomization. A clinical events committee will adjudicate all component events for the primary endpoint. The number and percentage of participants with the composite endpoint at the 90-day visit after the randomization will be summarized and compared according to assigned transfusion strategy (analysis by intent to treat) using Pearson χ^2 test. Another analysis will compare primary endpoint between the two transfusion strategies stratified by clinical sites using the Cochran-Mantel-Haenszel test (Table 16a-e). The test for differences between transfusion strategies in the primary outcome will be conducted at an overall α -level of 0.05. Additional analysis will be conducted using logistic models to adjust for other clinical factors, such as age, RCRI, and nadir Hb. The interactions of the intervention with age, RCRI and nadir Hb will also be considered.

Odds ratio and 95% confidence interval (CI) will be presented using SAS PROC GENMOD or PROC LOGISTIC. Assumptions of the model including linearity in the logit of the composite event risk for continuous variables will be checked. We will assess goodness-of-fit using the statistic -2 log likelihood, which has a chi-square distribution under the null hypothesis that all the explanatory variables in the model are not associated with the outcome

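### The protocol's additional logistic model contains treatment interactions but rejects on the treatment coefficient alone; with no centring stated, that coefficient is the effect at age 0 and Hb 0

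*Protocol*

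**What the plan says.** **Protocol XVI.E.2.** The primary comparison is an unadjusted Pearson chi-square test by intention to treat. A logistic model follows as an additional analysis. Its covariates are age, RCRI, nadir Hb and site, plus "the interactions of testing factor with age", RCRI and nadir Hb. The printed equation has one coefficient for treatment (β1) and one for each interaction (β6, β7, β8). The decision rule is: "If the coefficient for treatment effect is significant, then the null hypothesis will be rejected". Protocol XVI.E.3, E.4 and E.5 and Table 4 carry the interaction terms into the secondary, tertiary, quantile-regression and Cox models.

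**SAP 7.1.** The equation is gone, and the text says: "The interactions of the intervention with age, RCRI and nadir Hb will also be considered". A coefficient rule remains: "if the coefficient for intervention effect is significant (i.e., the confidence interval for the odds ratio does not include 1"), then the null of no intervention effect, adjusted for the other covariates in the final model, is rejected. The Table 17 shell has rows for treatment, age, RCRI classes 1 to 4 and nadir Hb, and none for interactions. SAP 7.2 to 7.4 list only age, RCRI and nadir Hb for the secondary, tertiary and Cox models. One leftover transfusion-by-age row stands in the Table 23 shell, under 90-day mortality.

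**The concern.** Once treatment interacts with a covariate, the treatment coefficient is no longer an overall effect. It is the effect where every interacting covariate equals zero or its reference level. Neither document says where zero lies for age or Hb. On the natural scales it is age 0 and Hb 0, whereas the trial enrols adults older than 18 and expects nadir Hb of 6-9 gm/dl in the restrictive arm.

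The protocol nevertheless attaches rejection of the null to that coefficient. An analyst who follows it literally would report an odds ratio without clinical meaning and a test that almost never detects the planned effect. Printed beside a positive chi-square result, it could be taken as evidence that the finding does not survive adjustment. Another analyst following the Table 17 shell would report a different adjusted odds ratio from the same data.

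**Working it through.** **Inputs from the documents.** Significance level (Protocol XVI.E): "All statistical tests will be two-sided and the primary outcome will be tested at 5% level of significance". Sample size (Protocol XVI.B): "a sample size of 1444 will be required at 90% power, 5% type-I error rate and with a two-sided test". Event rates (same section): "we assume that 30% rate for the primary endpoint can be anticipated in the restrictive transfusion group", and "We also assume a 25% reduction or 22.5% event rate in the liberal group".

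**The plan's own figure.** With pooled p = (0.30 + 0.225)/2 = 0.2625 and no continuity correction:

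n per arm = [1.960·√(2 × 0.2625 × 0.7375) + 1.2816·√(0.30 × 0.70 + 0.225 × 0.775)]² / 0.075² = (1.2196 + 0.7945)² / 0.005625 ≈ 721.2, rounded up to 722.

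So N = 1444, and 1444/0.95 = 1520. Both figures reproduce. They rest on the unadjusted test.

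**What the coefficient estimates.** In the printed model the treatment log odds ratio for a given patient is

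β1 + β6·age + β7·RCRI + β8·Hb.

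β1 alone is its value at age 0 and Hb 0, and at RCRI 0 or the reference class.

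**Assumptions not in the documents.** Mean age 66-70 (SD 8-12); mean nadir Hb 8.5-9.0 gm/dl (SD 0.6-1.2); RCRI classes 1 to 4 in proportions 20/35/30/15%; moderate prognostic effects; the same treatment odds ratio for everyone, set to give 30% versus 22.5%. Site was left out for simplicity. The unadjusted log odds ratio is ln(0.225/0.775) − ln(0.30/0.70) = −0.39; with covariates it is about −0.40 to −0.41.

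**Why the standard error is large.** Take age 68 (SD 8), Hb 8.7 (SD 0.8) and RCRI mean 2.4 (SD 0.97). With centred terms the SE of the treatment coefficient is 0.125. Each interaction SE is roughly 0.125 divided by the covariate SD. Moving back to zero adds (mean × interaction SE)²:

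- age: (68 × 0.125/8)² = 1.129
- Hb: (8.7 × 0.125/0.8)² = 1.848
- RCRI: (2.4 × 0.125/0.97)² = 0.096
- centred part: 0.125² = 0.016

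The sum is 3.09 and its square root 1.76. The full expected-information calculation gives 1.77.

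**Power and sign.** Power is Φ(|b|/SE − 1.96) + Φ(−|b|/SE − 1.96). For b = −0.402 and SE 1.767 the ratio is 0.2275, so power is Φ(−1.73) + Φ(−2.19) = 0.042 + 0.014 = 5.6%. The chance of the wrong sign is Φ(−0.2275) = 41%.

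| Model, N = 1444 | SE of treatment coefficient | Power over the assumed ranges |
|---|---|---|
| Interactions, not centred | about 1.2-2.3 | 5.4%-6.3% |
| Interactions, centred | about 0.12-0.13 | 89%-90% |
| Main effects only | about 0.12 | 91% |

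The two lower rows assume that nadir Hb is distributed alike in both arms. RCRI as linear or as categorical gave nearly the same results. By formula, the wrong-sign chance runs from Φ(−0.411/1.206) = 37% to Φ(−0.399/2.274) = 43%. Direct simulation over similar ranges gave 35-42%, with power of about 6-7%.

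**Simulated rejection rates, 1000 trials per row.**

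| Truth | Not centred | Centred | Main effects | Joint 4-df test |
|---|---|---|---|---|
| No effect for anyone | 5.1% | 4.9% | 4.3% | 5.1% |
| Planned effect, same for all | 5.6% | 91.2% | 91.4% | 76.9% |
| Zero effect at covariate means, age interaction 0.3 per 10 years | 22.6% | 5.2% | 6.5% | 34.3% |
| Same, 0.5 per 10 years | 50.2% | 6.1% | 9.7% | 75.6% |

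So the rule misses the planned effect. It can also reject often when there is no effect at the covariate means.

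**The case against.** The strongest reply is that little depends on this model. The Pearson test is primary and the logistic model additional. The SAP, to which Protocol XVI.H defers detail, drops the equation, only considers the interactions, and shows main effects in the shells for Tables 17, 19, 21, 27 and 28. Its rejection rule concerns an adjusted null within the logistic analysis, so it does not compete with the chi-square decision. All of that stands, and it limits the point to a supplementary analysis.

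It does not remove the point. SAP 7.1 gives no criterion for keeping an interaction. It allows variables to be added when fit is poor, and it applies the coefficient rule to whatever model results. SAP 7.2 to 7.4 refer back to the primary analysis. Protocol XVI.H requires deviations from the protocol to be specified in the SAP, and the SAP text does not say that the interactions were dropped.

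Three stronger readings are tempting but unsupported:

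- **That the plan prescribes uncentred covariates.** It is silent on scaling. The fault is that a pre-specified rule depends on an unstated choice.
- **That the coefficient refers to RCRI 0.** RCRI is a class, listed 1 to 4 in the SAP shells. The single RCRI coefficient in the protocol equation proves nothing, because site also gets only one. If RCRI is categorical, the coefficient refers to its reference class.
- **That the trial has about 5% power, or that its error rate is compromised.** Neither follows. The low power belongs to one coefficient in an additional model, and under a complete null that test keeps its size (5.1%).

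**Conclusion.** The point holds for the protocol text as written and, conditionally, for the SAP. If the printed interaction model is fitted to covariates on their natural scales, the coefficient on which the null is rejected lies outside the trial population. Its power at the planned effect is about 5-7%, its SE about 1.2-2.3, and its sign wrong in about 35-43% of trials. Centred terms or main effects alone give about 90%.

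These figures rest on assumed covariate distributions, a homogeneous effect and no site terms. The near-5% power held in every scenario tried. The 90% comparator is less secure. If nadir Hb is taken after randomization and is 0.8 gm/dl higher in the liberal arm, power falls to 76-87% with centred terms and 77-88% with main effects. Whether nadir Hb is a post-randomization covariate is a separate issue, which centring does not settle.

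The primary Pearson test, its alpha and N = 1444/1520 are unaffected. This should be corrected before the adjusted analysis is run, but it does not threaten the primary result.

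**What to change.** - State in SAP 7.1 and Protocol XVI.E.2 that the adjusted treatment effect and its test come from the main-effects model already shown in the Table 17 shell.
- Restrict the coefficient rejection rule to that model.
- Examine each treatment interaction separately, by its own interaction test, with age and Hb centred and the RCRI reference class stated.
- Align the protocol's secondary, tertiary, quantile-regression and Cox wording with the SAP, and record the change as a deviation, as Protocol XVI.H requires.
- Remove the leftover transfusion-by-age row from the Table 23 shell.

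An alternative is to keep the interactions, centre age and nadir Hb, state the RCRI reference or weighting, and test one pre-specified average contrast. In the calculations above, centring restored 89-90% power. Taking the effect from the main-effects model is simpler and matches the existing shell.

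The cost is wording in two documents and one table shell. Data collection, sample size and trial conduct do not change.
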